Study Design: Phase 3 multi-center, outpatient, randomized, double-blind, placebo-controlled study of LY2951742 300 mg administered every 30 days compared with placebo for the prevention of chronic cluster headache. The study has 5 study phases (SP): SP I (screening/washout phase), SP II (pre-randomization diary phase), SP III (treatment phase), SP IV (optional open-label extension phase), and SP V (post-treatment follow-up phase).

Diagnosis and Main Criteria for Inclusion and Exclusions: The planned patient population includes adult outpatients (18 to 65 years of age inclusive) who meet the *International Classification of Headache Disorders, Third Edition, beta version*, or *ICHD-3 (ICHD-3 2013)*, diagnostic criteria for Chronic Cluster Headache and, during baseline assessment, have a maximum of 8 attacks per day and a minimum of 8 attacks. Patients should also be able to distinguish cluster headache attacks from other headaches (that is, tension-type headaches, migraine) and not be anticipated to spontaneously remit during the double-blind treatment phase in the opinion of the investigator. Patients are excluded from study participation if they are currently enrolled in another clinical trial, are using or have used CGRP or nerve growth factor (NGF) antibodies, have a lifetime history of migraine variants that could implicate or could be confused with ischemia, are taking indomethacin and/or are suspected of having another distinct trigeminal autonomic cephalgia, or have had botulinum toxin type A or type B administered in the head or neck area within 4 months of SP II.

Investigational Product, Dosage, and Mode of Administration or Intervention: subcutaneous injections of LY2951742 300 mg administered every 30 days as three 1-mL injections.

Reference Therapy, Dose, and Mode of Administration or Comparative Intervention: subcutaneous injections of placebo (0.9% Sodium Chloride Injection, USP; volume matched) administered every 30 days during SP III.

Planned Duration of Treatment: 64 weeks + up to 16 weeks post-treatment follow-up

Screening/washout phase: up to 65 days

Pre-Randomization Diary phase: approximately 2 weeks

Treatment phase: 12 weeks

Open-label Extension phase: approximately 52 weeks

Post-treatment follow-up phase: 16 weeks

Criteria for Evaluation:

Effectiveness:

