(Visits 4 and 7) with the patient approximately 1 week after the first two IP administration visits during SP III to collect spontaneously reported AEs. At Visit 5, the patient will come into the office for the collection of blood samples 2 weeks after the first dose. During SP III, the patient will continue to record his or her cluster headache attack information daily in the ePRO diary.

- For patients who discontinue early in SP III, they should enter SP V.
- For patients who complete SP III, SP IV is an optional 1-year exposure, open-label treatment phase which is described below.
- For patients who choose not to enter SP IV, they should enter SP V.

During SP IV, the unblinded site personnel will continue to prepare the IP for each patient. All patients who enter SP IV will receive open-label monthly injections of LY2951742. All study procedures at Visit 9 must be completed prior to patients receiving the first dose of LY2951742 in SP IV. Patients and investigators will remain blinded to the SP III treatment assignments during SP IV. Each dose of IP will be administered as 3 SC injections at office visits: Visits 9 and 11 through 21. Since placebo patients will be transitioning to LY2951742 at Visit 9, all patients should remain in the office for 30 minutes for observation after administration of IP. Also, during SP IV, some patients may transition to LY2951742 300 mg supplied in 3 prefilled syringes with each syringe containing 100 mg. These patients should remain in the office for 30 minutes for observation after the first prefilled syringe injection. All patients will continue to record his or her cluster headache attack information daily in the ePRO diary until Visit 11.

Study Phase V is a 16-week post-treatment phase for safety follow-up.

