7.2. Discussion of Design and Control

This study is a double-blind, placebo-controlled, multi-center study consisting of 5 SPs: a screening phase, a pre-randomization diary phase to assess cluster headache attack frequency for eligibility, a double-blind, placebo-controlled treatment phase to assess treatment outcomes, an open-label extension phase, and a post-treatment follow-up phase to allow for safety monitoring after LY2951742 treatment is stopped.

The proposed duration of the double-blind treatment phase is 3 months, with the primary endpoint assessed from Weeks 1/2 through Weeks 11/12 after the first IP dose. The length of the randomized, double-blind treatment phase (3 months) is believed to be a sufficient duration to assess the efficacy of a cluster headache prevention medication given the mechanism and observed onset of action for CGRP antibodies in migraine (Dodick et al. 2014a, 2014b). The primary measure of weekly cluster headache attack frequency and use of placebo-control is consistent with current published International Headache Society guidelines (IHS 1995). Moreover, a placebo-controlled study with a duration longer than 3 months may not be tolerated by patients suffering from chronic cluster headache.

Because of the severity of patients suffering from chronic cluster headache, a requirement of patients to washout of all preventive treatments before study entry is not feasible. Therefore, the study allows use of certain allowed preventive treatments during the study as long as the patient

is on a stable dose for at least 2 months prior to the pre-randomization diary phase (SP II) and remains on that dose throughout the study.

8. Study Population

All patients must meet the following selection criteria. Eligibility of patients for study enrollment will be based on the results of a screening medical history, physical examination, clinical laboratory tests, ECG, and cluster headache history during SP I and SP II, as described in the Inclusion and Exclusion Criteria sections below. The nature of any co-morbid conditions present at the time of the physical examination and any pre-existing conditions must be documented.

Individuals who do not meet the criteria for participation in this study (screen failure) may be considered for rescreen once, for selected criteria, with approval from Lilly Medical, as described in Section 8.3.

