12.2. Statistical and Analytical Plans

12.2.1. General Considerations

Unless otherwise specified, efficacy analyses will be conducted on an ITT population, which include all patients who are randomized and receive at least 1 dose of IP. Patients in the ITT population will be analyzed according to the treatment group to which they were randomized. Safety analyses for SP III and exposure will be conducted on the safety population, which also includes all patients who are randomized and receive at least 1 dose of study drug. However, patients will be analyzed by actual study treatment received most often (modal treatment; placebo or LY2951742) during the double-blind treatment phase. Safety analyses during LY2951742-treated time and LY2951742-treated time plus post-treatment time will be conducted on the LY2951742-treated population, which includes all patients who receive at least 1 dose of LY2951742. When mean change from baseline is assessed, the patient will be included in the analysis only if he/she has a baseline and a post-baseline measurement. Additional analyses population for analyses of study Phase IV and Phase V will be described in the SAP.

Baseline will be the last 14 days in the eligibility report (pre-randomization diary phase). An additional baseline defined at Visit 9 (the first visit of the open-label phase) may be used for some analyses. This, in addition to details for handling missing data, will be further outlined in the SAP.

Treatment effects will be evaluated based on a 2-sided significance level of 0.05 for all the efficacy and safety analyses. The 95% CIs for the difference in least-square means (LSMeans) between treatment groups will be presented. Adjustments for multiple comparisons for the analyses corresponding to the primary and gated secondary objectives are described in the sections on the primary and secondary efficacy analyses below. There will be no adjustments for multiplicity for analyses of other data.

Any change to the data analysis methods described in the protocol will require an amendment ONLY if it changes a principal feature of the protocol. Any other change to the data analysis methods described in the protocol, and the justification for making the change, will be described in the clinical study report.

Additional exploratory analyses of the data will be conducted as deemed appropriate.

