^a Selected tests may be obtained in the event of a treatment-emergent hepatic abnormality and may be required in follow-up with patients in consultation with the Lilly, or its designee, clinical research physician. See [Attachment 3](#) for more details regarding specific hepatic monitoring tests. If the patient has discontinued the trial and returns for hepatic follow-up, the site should use the 800 series as the visit designation.

Study Schedule, I5-Q-MC-CGAM SP V

Study Phase	SP V		ET	
Description	Follow-Up		ET	Comments
Visit	23	24		
Visit Day	510	570		
Month	17	19		
Interval (days) since previous visit	60	60		
Interval allowance (days)	+/-8	+/-8		
ECG		X	X	To be collected prior to blood draws and dosing. Patients must be supine for 5-10 min before collection and remain supine but awake during collection.
Weight		X	X	
Vital signs	X	X	X	Vital signs will also be taken at unscheduled office visits. Vital signs include body temperature, blood pressure, and pulse. Blood pressure and pulse will be measured in triplicate in the sitting position and should be measured prior to blood draws. Blood pressure will be assessed by utilizing a calibrated machine that will be provided to the sites.
Hematology		X	X	
Clinical chemistry ^a		X	X	Except for V1, chemistry labs require fasting (no food or drink, except water, for at least 8 hrs).
Urinalysis		X	X	
HbA1C		X	X	
Serum Pregnancy		X	X	Female patients only
Immunogenicity	X	X	X	Immunogenicity samples must be collected prior to dose administration if the visit is a dosing visit. Samples will be taken in the event of early termination. The timing of samples will be recorded.
	■	■	■	CCI
Plasma Storage Sample (K+/EDTA)	X	X	X	The timing of the samples will be recorded. These samples will be collected in a K+/EDTA container.
PK sampling	X	X	X	The timing of the samples will be recorded.
RNA sample storage	X	X	X	Sample must be collected in a Tempus tube.
PGI-I		X	X	
C-SSRS/SHSF, SHFU	X	X	X	Should also be completed at scheduled and unscheduled office visits.
Recording of AEs	X	X	X	
Concomitant medications	X	X	X	

Study Schedule, I5-Q-MC-CGAM SP V

Abbreviations: AE = adverse event; CCI

C-SSRS = Columbia-Suicide

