5.5.1.5. Analysis Populations

Four analysis populations including ITT population, safety population, open-label population, and GMB-treated population are defined in Section [5.5.1](#).

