5.5.9. Safety Analyses

The safety analyses will be conducted on the safety population during the double-blind treatment phase (SP III), and on the GMB-treated population during the GMB-treated time (SP III/IV combined) and the GMB-treated time plus post-treatment time (SP III/IV/V combined). All the safety analyses outlined below will be conducted as long as the safety measures were collected at the specific study phase.

The safety and tolerability of treatment will be assessed by summarizing the following:

- adverse events
 - treatment-emergent adverse events
 - by PT
 - by PT nested within SOC
 - by maximum severity
 - serious adverse events by PT nested within SOC
 - adverse events leading to discontinuation by PT nested within SOC
 - adverse events of special interest
- suicide-related thoughts and behaviors by C-SSRS
- vital signs and weight
- laboratory measurements
- electrocardiograms
- antibodies (ADA and NAb)

The baseline and postbaseline for all safety measures are described in [Table CGAM.5.3](#) unless specified otherwise. For SAEs, only events with a start date during the post-baseline phase will be accounted for the corresponding study phase analysis.

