Above analyses was only described for SP III, for the analyses including SP IV and SP V, the baseline and postbaseline definition for each of the analyses above is summarized in [Table CGAM.5.5](#).

Table CGAM.5.5. Baseline and Post-Baseline Definition for Treatment-Emergent Suicidal Analyses for GMB-treated Population

Analyses	Study Phase	Baseline	Post-baseline

 Treatment-emergent suicidal ideation compared to recent history Treatment-emergent serious suicidal ideation compared to recent history Emergence of serious suicidal ideation compared to recent history 	III/IV	
Visit 1 to 3 excluding lifetime for GMB-treated patients in SP III;
 
Visit 1 to 9 excluding lifetime for placebo treated patients in SPIII.
	
Visits 3.01 to 22 for GMB-treated patients in SP III;
 
Visits 9.01 to 22 for placebo treated patients in SP III.

	III/IV/V	
Visit 1 to 3 excluding lifetime for GMB-treated patients in SP III;
 
Visit 1 to 9 excluding lifetime for placebo treated patients in SPIII.
	
Visits 3.01 to 24 for GMB-treated patients in SP III;
 
Visits 9.01 to 24 for placebo treated patients in SP III.

 Treatment-emergent suicidal ideation compared to all prior history Treatment-emergent serious suicidal ideation compared to all prior history Emergence of serious suicidal ideation compared to all prior history Emergence of suicidal behavior compared to all prior history 	III/IV	
Visit 1 to 3 including lifetime for GMB-treated patients in SP III;
 
Visit 1 to 9 including lifetime for placebo treated patients in SPIII.
	
Visits 3.01 to 22 for GMB-treated patients in SP III;
 
Visits 9.01 to 22 for placebo treated patients in SP III.

	III/IV/V	
Visit 1 to 3 including lifetime for GMB-treated patients in SP III;
 
Visit 1 to 9 including lifetime for placebo treated patients in SPIII.
	
Visits 3.01 to 24 for GMB-treated patients in SP III;
 
Visits 9.01 to 24 for placebo treated patients in SP III.

Improvement in suicidal ideation at endpoint compared to baseline	III/IV	
Last non-missing measure prior to or at visit 3 for GMB-treated patients in SP III;
 
Last non-missing measure prior to or at visit 9 for GMB-treated patients in SP III.
	
Last value during Visits 3.01 to 22 for GMB-treated patients in SP III;
 
Last value during Visits 9.01 to 22 for GMB-treated patients in SP III.

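### Post-treatment safety data (SP V) are summarised only inside the pooled SP III/IV/V window, so some events that return or recur after galcanezumab stops are missed or cannot be tied to SP V

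*SAP*

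**What the plan says.** Protocol 7.2 describes SP V as "a post-treatment follow-up phase to allow for safety monitoring after LY2951742 treatment is stopped", and Protocol 7.1 says "Study Phase V is a 16-week post-treatment phase for safety follow-up". Attachment 1 schedules AE recording and C-SSRS at both SP V visits (23 and 24).

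On populations, Protocol 12.2.1 states: "Additional analyses population for analyses of study Phase IV and Phase V will be described in the SAP". SAP 5.5.1.5 says "Four analysis populations including ITT population, safety population, open-label population, and GMB-treated population are defined". Table CGAM.5.2 assigns the GMB-treated population to two windows, SP III/IV and SP III/IV/V.

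SAP 5.5.9 has three safety windows: SP III, SP III/IV, and "the GMB-treated time plus post-treatment time (SP III/IV/V combined". Protocol 12.2.10 sets out the same scheme. In the widest window, the TEAE baseline (Table CGAM.5.3) is Visits 1-3 before dosing for patients randomised to galcanezumab, and Visits 1-9 before open-label dosing for patients randomised to placebo. Post-baseline then runs unbroken to Visit 24. The C-SSRS emergence endpoints (5.5.9.1.2, Table CGAM.5.5) follow the same pattern, with post-baseline "Visits 3.01 to 24 for GMB-treated patients in SP III". SAEs and discontinuations due to AEs have no baseline. Results in the GMB-treated population are descriptive only (5.5.9.1), and continuous safety measures are summarised for SP III only (5.5.9.2).

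**The concern.** The off-drug question that SP V was set up to address has no table of its own. Someone who wants to know what happened after stopping must compare the SP III/IV and SP III/IV/V tables. That comparison has three weaknesses.

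- Both tables use the GMB-treated population, which includes patients who never entered SP V. The difference is therefore a count without the right denominator and without a rate.
- The baseline precedes the first galcanezumab dose. An event that was present before drug, eased on drug and came back after stopping is judged against its pre-drug level, not against its level when treatment ended.
- Both tables count patients. A patient who already had the event on drug adds nothing when it happens again in SP V.

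At stake is whether a rise in AEs, or a return of suicidal ideation, after stopping would be visible. C-SSRS ideation and behavior is a secondary safety objective (Protocol 6.2.2).

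**Working it through.** **Schedule.** The synopsis gives "Planned Duration of Treatment: 64 weeks + up to 16 weeks post-treatment follow-up". This reproduces: 12 + 52 = 64 weeks, and Visit 22 at Day 450 is 450/7 = 64.3 weeks. Dosing agrees: 3 + 12 = 15 doses x 30 days = 450 days. For SP V, Attachment 1 has "Visit Day 510 570", so 570 - 450 = 120 days, or 17.1 weeks. The text says 16 weeks (112 days). The two should be reconciled, but the result hardly depends on which is used.

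**Share of the pooled window, full completers.**
- Randomised to galcanezumab: 120/(450 + 120) = 21%. With 112 days: 112/562 = 20%.
- Placebo first, galcanezumab from Visit 9 (Day 90): 120/(360 + 120) = 25%. With 112 days: 112/472 = 24%.

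**What the planned tables register.** The TEAE rule (SAP 5.5.9.1.1) needs post-baseline maximum severity above the baseline maximum for the same lowest level term. C-SSRS items and composites (5.5.9.1.2) are yes/no at any time, without a baseline comparison. SAEs need only a start date in the window (5.5.9).

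| Event in SP V | SP III/IV table | SP III/IV/V table | Recovered by subtraction? |
|---|---|---|---|
| AE term not seen before or on drug | no | yes | yes |
| SAE, term not an SAE on drug | no | yes | yes |
| Ideation 2 before drug, 0 on drug, 2 at Visit 24: ideation composite | no | yes | yes |
| Same patient: emergence endpoints | no | no | no |
| Same patient, last pre-dose score 2: improvement endpoint | improved | not improved | as a net change |
| Non-serious AE, moderate before drug, absent on drug, moderate in SP V | no | no | no |
| Term seen on drug, same severity again in SP V | yes | yes | no |

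Worsening in SP V of a term already seen on drug shows only as a shift in the maximum-severity table.

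**Dilution (illustrative).** The documents give no event rates, so these are assumed, constant within phase, for a completer randomised to galcanezumab.
- Rate doubled in SP V: pooled rate ratio (450 + 2 x 120)/570 = 1.21. Tripled: (450 + 3 x 120)/570 = 1.42.
- At 10 per 100 patient-years, percentage = 1 - exp(-0.10 x days/365). Pooled: 14.5% with no change (570 days), 17.2% with doubling (690 equivalent days). SP V only: 3.2% (120 days) and 6.4% (240 equivalent days).
- Over on-drug rates of 0.25% to 5% per month and 2- to 5-fold increases, the ratio of percentages (with versus without the increase) is 1.1 to 1.8 in the pooled table and 1.8 to 4.9 in an SP V-only table.

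**Recurrence.** If SP V events are independent of on-drug events, the share of SP V-affected patients who add nothing to the pooled count equals the 15-month on-drug incidence, 1 - exp(-15h). For h = 0.25%, 1%, 3% and 5% per month this is 4%, 14%, 36% and 53%.

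**The case against.** The case for leaving the SAP alone is strong in several respects, and most of it stands.

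- **The pooling is deliberate.** The SAP revision history says overall estimates across phases were judged more medically useful than by-phase estimates. The protocol specifies the same windows.
- **No commitment was broken.** A reader might infer from Protocol 12.2.1 that a promised SP V population was dropped. That sentence only sends the description of populations to the SAP, and Table CGAM.5.2 supplies the GMB-treated population for a window that includes SP V.
- **Harm after stopping is largely counted.** A reader might infer that SP V events go uncounted. The table above shows otherwise for SAEs, first-onset AEs and C-SSRS items and composites, including self-injurious behavior without suicidal intent.
- **The Introduction does not link attacks to suicidality.** It reports self-injurious behavior during attacks. Return of attacks would not be measured in SP V in any case: the diary ends at Visit 11 (Protocol 10.1.1), and lack of drug effect is not an AE (10.2.1).
- **SP V is not otherwise unreported.** Disposition and concomitant therapy are shown for SP V, the hepatic listing covers all phases, the hypersensitivity listing gives timing from the latest dose, and TE ADA is reported for a follow-up cohort.
- **An SP V table would be uncontrolled.** Percentages alone could mislead: in the example above, 6.4% over 120 days would sit beside 1 - exp(-0.10 x 450/365) = 11.6% over 450 days, and a doubling would not be obvious.

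The last point is answered by exposure-adjusted rates (20 against 10 per 100 patient-years in that example). The others narrow the concern. They do not supply an SP V denominator or rate, or recover the three cases that subtraction cannot.

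**Conclusion.** The concern holds in a limited form. SP V safety outcomes are summarised only in a window of which SP V is 21% to 25% for full completers, with no SP V denominator or rate. Three kinds of event are missed or cannot be attributed to SP V: a non-serious AE returning at its pre-drug severity; ideation returning to its pre-drug level, in the emergence endpoints only; and recurrence of an event already seen on drug.

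The documents do not support reading this as a failure to count post-stopping harm in general, or as a departure from the protocol. It is an inexpensive gap to close before final lock. The time shares rest on the protocol schedule and full completion; early discontinuers have less on-drug time. The dilution ratios rest on assumed rates and multipliers and show direction and plausible size only.

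**What to change.** Keep the pooled tables. Add to SAP 5.5.9 a descriptive SP V-only summary for patients with at least one galcanezumab dose who enter SP V. Use the number entering SP V as denominator, and give exposure-adjusted rates beside the percentages. Show two sets:

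- (a) all AEs and SAEs with a start date in SP V, and all C-SSRS ideation, behavior and self-injury items reported in SP V, regardless of earlier occurrence;
- (b) events and ideation that are new or worse than status at the end of treatment, taken as the last SP III/IV assessment.

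The baseline in (b) should be end-of-treatment status, not the whole on-drug period. Under the maximum-severity rule, a term seen once in up to 15 months on drug would hide a recurrence at equal severity. Set (a) covers recurrences that (b) still excludes.

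The cost is a short SAP addition and one more set of tables at final lock, when SP IV and SP V outputs are rerun anyway (SAP 5.8.1.2 and 5.8.1.3). No new data, dose or clinical rule is involved. The downside is that the summary is small and uncontrolled, so it should be labelled descriptive only.
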